7. STATISTICAL ANALYSIS

For the data analysis, we will estimate frequencies of adverse events, central tendency and variability for patient's demographic characteristics, velocity, stride length, TUG and the UPDRS score. All analyses will be conducted using SAS (version 9.2, SAS Institute Inc., Cary, NC).

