PROTOCOL

Official Title: Deep brain stimulation effects on gait and balance in patients with Parkinson's disease

PI: [name] [name]

Document Date: January 4, 2016

NCT Number: NCT02022735

1. STUDY DESIGN AND SCHEMA:

Gait and balance problems are dopamine resistant features of Parkinson's disease (PD).

Deep brain stimulation of sub-thalamic nucleus (STN-DBS) is an established surgical method that improves motor symptoms and gait in PD, however it may produce unexpected freezing of gait and balance problems in some patients, presumably due to overstimulation and gait incoordination. The aim of this study is to identify the differential effects of unilateral STN stimulation versus bilateral stimulation on gait kinematics in patients with PD and associated gait dysfunction.

2. BACKGROUND AND RATIONALE :

Freezing of gait (FOG) and walking difficulties represent perhaps the most difficult challenges in the treatment of Parkinson's disease (PD). PD patients experience frequent difficulty initiating walking, shuffling and postural instability (Vu, Nutt et al. 2012). In spite of dopaminergic therapy, walking difficulties continue to progress and only rarely do non-dopaminergic treatments provide benefit. Deep brain stimulation of sub-thalamic nucleus (STN-DBS) improves motor scores, walking and FOG (St George, Nutt et al. 2010). In some patients, even after appropriate fine tuning of programming, walking and balance continue to be a problem. One explanation can be the progression of the disease, however in some cases the FOG appears soon after the DBS. This has been attributed to overstimulation and perhaps asymmetric stimulation in the networks involved in gait

control. Several studies have looked at the parameters of stimulation and have concluded that reducing the frequency of stimulation would ameliorate walking difficulties (Fasano, Herzog et al. 2011). Similarly, reducing the amplitude contralateral to the most affected side is associated with less FOG (Moreau, Defebvre et al. 2008).

A growing body of literature suggests that right-hemisphere circuitry seems to be more affected than the left in patients with FOG (Fling, Cohen et al. 2013) and that patients with worse symptoms on the left are more likely to develop postural instability gait dysfunction (PIGD) (Giladi, McDermott et al. 2001)

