3. OBJECTIVES

In this study we aim to evaluate the effects of differential STN stimulation on walking. We hypothesize that in patients with FOG, unilateral stimulation on the most affected hemisphere will ameliorate walking in a higher degree than bilateral stimulation. Functional asymmetry of STN was shown before by other studies (Castrioto, Meaney et al. 2011) and is thought that unilateral STN stimulation has effects that are similar with bilateral STN on UPDRS motor scores, effect called dominant STN. Since the effects of unilateral stimulation on walking are not completely understood, we plan to determine if unilateral stimulation has differential effects on gait kinematics.

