4. STUDY POPULATION

Inclusion criteria are: patients with idiopathic PD with Hoehn and Yahr Stage 1-3 that have undergone STN-DBS and had developed difficulty walking 6-12 months after the DBS on stable dosage dopamine agonist/levodopa, expected to remain on the same dosage of treatment for the next 3 months; age 45-70.

Exclusion criteria are: past medical history of seizures, renal insufficiency and history of cardiac arrhythmia, previous DBS, severe arthritis, women of childbearing potential, dementia and less than 45 and over 70 years old.

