5. MEASUREMENTS AND EVALUATION

This study is meant to see if there is improvement in gait or freezing of gait after changes in the stimulation parameters.

- In the first part of the study subjects (1 visit) will be randomly assigned to four different stimulation parameters: both stimulators ON, both stimulators off, right stimulator ON, left stimulator ON. We will assess participants' gait using clinical scales as well as wearable sensors attached to the body. Assessments will be done one hour after each change in the stimulation parameters.
- In the second part of the study that participants may be asked to participate in, changes in the frequency of stimulation and contact stimulation will be performed. Four different stimulation settings will be tested. In this part evaluations will be done.

PART 1

Screening: At this visit, the study investigator will discuss the details of the research study and the consent form with the study participant.

The following procedures will also be completed:

- Sign informed consent form.
- Collection of a complete medical history and a neurological exam.
- United Parkinson's disease rating scale (UPDRS) will be performed by a Movement Disorder Specialist to assess the severity of Parkinson's disease.

- Timed Up and Go test (TUG) - a mobility test that is used to measure the basic mobility skills of people who are elderly or have neurological conditions such as PD and it includes a sit-to-stand component as well as walking 3m, turning and returning to the chair.
- Freezing of Gait Questionnaire (FOGQ) which is a self-report questionnaire consisting of 16 items regarding falls and walking problems.
- Gait analysis using wearable sensors (Mobility Lab) to measure the walking speed and step length.

If study subjects meet the eligibility criteria, they will be asked to sign the informed consent and asked to come to clinic for part 1 or for part 2 of the study without taking their Parkinson's medication for 12 hours.

Visit 1 Changes to the DBS stimulator will be done every 60 minutes for 4 hours in a random order.

- Bilateral stimulators ON, bilateral stimulators OFF, Right ON-Left OFF, Right OFF-Left ON.
- UPDRS scale
- Gait analysis using wearable sensors (Mobility Lab) to measure the walking speed and step length.

This visit will take about 5 hours. At the end of the visit study participants will go home with their initial settings.

PART 2

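### Section 7 is descriptive only: it sets no paired between-setting contrast for Part 1 and no rule linking right-ON and left-ON to the most affected hemisphere named in the Section 3 hypothesis

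*Combined protocol and SAP*

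**What the plan says.** **Aim (Section 1).** The study is to "identify the differential effects of unilateral STN stimulation versus bilateral stimulation on gait kinematics".

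**Hypothesis (Section 3).** "We hypothesize that in patients with FOG, unilateral stimulation on the most affected hemisphere will ameliorate walking in a higher degree than bilateral stimulation". The section closes more loosely: "we plan to determine if unilateral stimulation has differential effects on gait kinematics".

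**Design (Section 5, Part 1, Visit 1).** Each patient has both stimulators on, both off, right only and left only, in random order within one visit and with 60 minutes per setting. UPDRS and sensor-based walking speed and step length are recorded. The unilateral settings are identified by anatomical side only.

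**Population (Section 4).** Entry requires an STN-DBS patient who "had developed difficulty walking 6-12 months after the DBS". FOG itself is not an entry criterion.

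**Analysis (Section 7).** One sentence states what will be computed: "we will estimate frequencies of adverse events, central tendency and variability for patient's demographic characteristics, velocity, stride length, TUG and the UPDRS score". The only other sentence names the software.

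**Nearest text to a side rule (Section 2).** The background says that "right-hemisphere circuitry seems to be more affected than the left in patients with FOG" and that "patients with worse symptoms on the left are more likely to develop postural instability gait dysfunction". These describe groups of patients. They do not classify an individual's hemispheres.

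**The concern.** The aim and the hypothesis are comparisons within a patient, and Part 1 collects the data for them. The analysis plan then stops at summaries, and does not even say that these are made per setting. Three things are missing.

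- There is no between-setting difference, interval or model, so no comparison comes with a measure of its precision.
- There is no rule that turns right-ON and left-ON into most-affected and less-affected unilateral stimulation. Where the most affected hemisphere differs between patients, a right-ON mean mixes patients stimulated on that hemisphere with patients stimulated on the other.
- There is no statement whether the comparison concerns patients with FOG, as in the hypothesis, or everyone enrolled for walking difficulty.

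Followed as written, the plan yields no estimate of the one hypothesis it states. It also leaves the labelling rule and the population open to being settled after gait results are known.

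**Working it through.** **1. Is there a figure to reproduce?** No. The documents give no sample size, alpha, power, effect size, SD, within-patient correlation or share of patients by affected side. Everything numerical below is illustration under stated assumptions.

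**2. What could by-setting summaries deliver?** Suppose Section 7 is read generously, as means and SDs for each setting. Subtracting the bilateral mean from the right-ON or left-ON mean gives a point estimate relevant to the Section 1 aim. Its precision cannot be recovered from the per-setting SDs. With equal SDs σ and within-patient correlation ρ, the SD of a paired difference is σ√(2(1−ρ)). Treating the settings as independent gives σ√2. The ratio of standard errors is √(1−ρ):

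| Assumed ρ | 0.3 | 0.5 | 0.7 | 0.9 |
|---|---|---|---|---|
| Paired SE / unpaired SE | 0.84 | 0.71 | 0.55 | 0.32 |

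The correlation is not among the planned summaries, so the paired uncertainty is lost.

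**3. Do by-setting summaries give the Section 3 contrast?** Let D be the true difference, most-affected unilateral minus bilateral. Let rD be the same difference for the less-affected side, and p the share of patients whose most affected hemisphere is the right. Assume that effects depend on the affected/less-affected label and not on right versus left as such. Then, as a share of D:

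- right-ON minus bilateral = p + (1−p)r
- left-ON minus bilateral = (1−p) + p·r

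| Right-ON / left-ON | r = 1 | r = 0.5 | r = 0 | r = −1 |
|---|---|---|---|---|
| p = 0.5 | 100% / 100% | 75% / 75% | 50% / 50% | 0% / 0% |
| p = 0.7 | 100% / 100% | 85% / 65% | 70% / 30% | 40% / −40% |
| p = 0.9 | 100% / 100% | 95% / 55% | 90% / 10% | 80% / −80% |

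For example, p = 0.7 and r = 0 gives 0.7 + 0.3 × 0 = 0.70 for right-ON and 0.3 + 0.7 × 0 = 0.30 for left-ON. Pooling the two unilateral settings does not help: the average of the two formulas is (1 + r)/2 at every p.

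Nothing is lost if both sides act alike (r = 1). Everything is lost at p = 0.5 if they act in opposite directions (r = −1). The documents do not exclude either case. The Section 2 remark on right-hemisphere circuitry makes p above 0.5 plausible in FOG, but gives no value.

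**4. Does the wording of a labelling rule matter?** Yes. Section 2 speaks in one place of hemispheres and in another of the side of symptoms. A rule that takes the worse body side without crossing to the opposite hemisphere would label every patient the wrong way round, and would estimate rD in place of D.

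**5. Is the rule supplied elsewhere?** No section defines how the most affected hemisphere is determined or how the settings are recoded. Section 7 reads as complete, with no sign of removed text.

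**The case against.** The best defence is that this is a small physiological study for which description is enough. Part 1 has one test visit, patients leave on their initial settings, and no alpha, power, primary endpoint or treatment decision is stated. This argument lowers the severity. It does not remove the point: the documents never call the study exploratory or a pilot, and Section 3 commits to a direction.

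A second defence is that right-ON and left-ON are of interest in themselves. Section 2 offers a right-hemisphere rationale, and the last sentence of Section 3 asks only about differential effects. That stands. Summaries by side are informative and should be kept, and if side itself modifies the effect, the formulas above do not hold. Such summaries still do not estimate the hypothesis about the most affected hemisphere.

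Third, the documents leave the meaning of most affected open. Section 3 ties the idea to a dominant STN, Section 2 to hemisphere and to symptom side. A reviewer should not choose for the sponsor. This stands too, so any particular rule is only an option.

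A reader might also infer that carryover between settings invalidates the comparison. The documents do not support that. Section 5 puts each assessment an hour after the switch, which may reduce carryover, though it does not exclude it.

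**Conclusion.** The point holds, as a should-fix. Section 7 contains no analysis that compares settings within patients, and no section links the right/left coding to the hemisphere in the hypothesis. By-setting means would at best serve the Section 1 aim crudely.

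The size cannot be stated from the documents. Under the label-dependent model, right-ON minus bilateral could show anything from all of the hypothesised difference (r = 1) to none of it (p = 0.5, r = −1), with half at p = 0.5 and r = 0. Both p and r are assumptions.

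Three stronger readings are not supported:

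- *The study cannot answer its question.* The within-patient data are planned; only the analysis is missing.
- *The side label or the population was chosen to suit the results.* The plan leaves room for that, but the documents do not show that it happened.
- *A mandatory correction is needed because a confirmatory test is undermined.* No confirmatory claim or power statement is made.

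**What to change.** Add to Section 7:

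- **One pre-specified Part 1 contrast.** Most-affected-hemisphere unilateral ON minus bilateral ON, within patient, on one named sensor outcome. Walking speed is an example, and it avoids the mismatch between step length in Section 5 and stride length in Section 7. Give a 95% confidence interval from paired differences, or from a mixed model with setting and period as fixed effects and patient as random.
- **A recoding rule with a tie rule**, fixed before any Visit 1 gait data are seen and preferably based on screening data. The hemisphere opposite the worse body side on the lateralised UPDRS items is one option. The sponsor should state the meaning it intends. It should also record the medication and stimulation state of the score used: the 12-hour instruction ("asked to come to clinic for part 1 or for part 2 of the study without taking their Parkinson's medication for 12 hours") concerns the test visits, and no state is given for screening. A label taken from Visit 1 scores would be weaker, since it is scored on the same day as the outcome with no rater blinding stated. The rule is for analysis only and changes no stimulation setting.
- **The analysis population.** Patients with FOG by a pre-set FOGQ definition, or all enrolled patients.
- **Descriptive tables by setting**, with right-ON and left-ON minus bilateral reported separately as secondary.
- **A short note on order.** Record the sequence for each patient and consider a sensitivity analysis with a preceding-setting term.

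The cost is some wording and a few lines of SAS. No patients or visits are added. The interval may be wide, since no sample size is given, and a preceding-setting term will be imprecise if few patients are enrolled.

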Screening: At this visit, the study investigator will discuss the details of the research study.

The following procedures will be completed:

- United Parkinson's disease rating scale (UPDRS) will be performed by a Movement Disorder Specialist to assess the severity of their Parkinson's disease.

- Timed Up and Go test (TUG) - a mobility test that is used to measure the basic mobility skills of people who are elderly or have neurological conditions such as PD that includes a sit-to-stand component as well as walking 3m, turning and returning to the chair.
- Freezing of Gait Questionnaire (FOGQ) which is a self-report questionnaire consisting of 16 items regarding falls and walking problems.
- Gait analysis using wearable sensors (Mobility Lab) to measure the walking speed and step length.
- The PI will review the medical records to assess if precise localization of the electrode contacts can be done using the CT scan that was performed post-operatively and will decide if an MRI of the brain is necessary to perform.

Visits 1, 2, 3 and 4

During these visits the stimulation settings will be changed to one of the following conditions: Low frequency stimulation-dorsal STN, Low frequency stimulation- ventral STN, High frequency stimulation- dorsal STN, High frequency stimulation –ventral STN

After each change the following tests will be performed:

- United Parkinson's disease rating scale (UPDRS) will be performed by a Movement Disorder Specialist to assess the severity of Parkinson's disease.
- Timed Up and go test (TUG) - a mobility test that is used to measure the basic mobility skills of people who are elderly or have neurological conditions such as PD and it includes a sit-to-stand component as well as walking 3m, turning and returning to the chair.
- Freezing of Gait Questionnaire (FOGQ) which is a self-report questionnaire consisting of 16 items regarding falls and walking problems.
- Gait analysis using wearable sensors (Mobility Lab) to measure the walking speed and step length.
- Clinical Global Improvement Scale

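### Section 7 plans descriptive summaries only, which give neither the contrast the hypothesis names (most affected hemisphere versus bilateral stimulation) nor the precision of any within-patient difference

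*Combined protocol and SAP*

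**What the plan says.** The question is comparative. Section 1 states: "The aim of this study is to identify the differential effects of unilateral STN stimulation versus bilateral stimulation on gait kinematics". Section 3 makes it directional for patients with freezing of gait: "unilateral stimulation on the most affected hemisphere will ameliorate walking in a higher degree than bilateral stimulation".

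Part 1 (Section 5) is a within-patient design completed in one visit. The Visit 1 text reads "Changes to the DBS stimulator will be done every 60 minutes for 4 hours in a random order", and the settings are "Bilateral stimulators ON, bilateral stimulators OFF, Right ON-Left OFF, Right OFF-Left ON". UPDRS and sensor gait are scheduled at that visit, and "Assessments will be done one hour after each change in the stimulation parameters".

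Section 7 is the only analysis text: "we will estimate frequencies of adverse events, central tendency and variability for patient's demographic characteristics, velocity, stride length, TUG and the UPDRS score", followed by the software. It contains no comparison between settings, paired difference, model, period term or confidence interval. It does not say that the summaries are given by setting, and it has no rule linking right and left to the more affected hemisphere.

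**The concern.** The plan does not compute the quantity it hypothesises about. There are two separate gaps.

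1. **Side.** Settings are labelled right or left, while the hypothesis concerns the more affected hemisphere. Which label applies differs from patient to patient, so the hypothesised contrast has to be assembled patient by patient. Nothing plans this, and a rule chosen after the gait results are seen could be chosen to suit them.
2. **Precision.** The same patients contribute to every setting. A mean and SD for each setting do not carry the within-patient correlation, so they do not show how precisely any difference between settings is known, or how far patients differ from one another in that difference.

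At stake is whether the study answers its own question from data it already plans to collect.

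**Working it through.** The plan gives no sample size, SD, correlation, effect size or error rate, so there is no figure of its own to reproduce. Results below that rest on assumed inputs are marked.

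**Is Part 1 within-patient?** The opening of Section 5 speaks of random assignment to four parameter sets, which alone could suggest parallel groups. The Visit 1 text settles it: the settings follow one another hourly in each patient, in random order.

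**Side labels.** Let M and L be the mean unilateral-minus-both-ON effects when the more and the less affected hemisphere is stimulated. Let p be the share of patients whose right hemisphere is the more affected. Suppose the effect depends only on which hemisphere is more affected (assumption).

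- Right-ON minus both-ON = pM + (1 − p)L, which differs from M by (1 − p)(L − M).
- Left-ON minus both-ON = (1 − p)M + pL, which differs from M by p(L − M).

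| p (assumed) | Right-ON: error as share of L − M | Left-ON: error as share of L − M |
|---|---|---|
| 0.5 | 50% | 50% |
| 0.6 | 40% | 60% |
| 0.7 | 30% | 70% |
| 0.8 | 20% | 80% |

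Averaging the two unilateral contrasts gives (M + L)/2 whatever p is. That addresses unilateral versus bilateral stimulation in general, but not M.

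**Precision, no inputs assumed.** For two settings with SDs s1 and s2 and within-patient correlation ρ, Var(D) = s1² + s2² − 2ρ·s1·s2. As ρ runs from 1 to −1, SD(D) runs from |s1 − s2| to s1 + s2 (0 to 2s if both equal s). The setting summaries cannot narrow this.

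**Precision, illustration.** Assume equal SDs s, and the ρ and n shown. SD(D)/s = √(2(1 − ρ)). The paired standard error divided by the one from treating settings as independent groups is √(1 − ρ). The ratio of 95% CI widths is [t(n − 1)/t(2n − 2)]·√(1 − ρ), where the t quantiles are 2.093/2.024 at n = 20 and 2.262/2.101 at n = 10.

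| ρ (assumed) | SD(D)/s | SE ratio | CI width ratio, n = 20 | CI width ratio, n = 10 |
|---|---|---|---|---|
| 0.3 | 1.18 | 0.84 | 0.87 | 0.90 |
| 0.5 | 1.00 | 0.71 | 0.73 | 0.76 |
| 0.7 | 0.77 | 0.55 | 0.57 | 0.59 |
| 0.9 | 0.45 | 0.32 | 0.33 | 0.34 |

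Pairing stops giving a narrower interval below ρ = 1 − (t(2n − 2)/t(n − 1))², which is 0.065 at n = 20 and 0.137 at n = 10. Above those values the independent-groups interval is the wider one.

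**The case against.** A small exploratory study may reasonably be descriptive and avoid formal tests. That stands, but a descriptive plan should still describe the quantity in its hypothesis, and a paired difference with an interval is estimation, not testing.

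Several stronger readings are tempting and are not supported:

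- *The plan yields no estimate at all.* With complete data and means by setting, the difference of two means equals the mean within-patient difference. A point estimate of right-ON or left-ON minus both-ON would then exist. Only the most-affected-hemisphere contrast would be missing. One could solve the two side equations for M if p were known, but finding p itself means classifying each patient, the solution fails at p = 0.5, and it needs the assumption that anatomical side has no effect of its own.
- *No valid interval could be built.* A reader could use s1 + s2 as an upper bound for the SD and obtain a conservative one.
- *The study would report a false benefit.* Treating settings as independent usually widens the interval. Section 7 does not propose that analysis either, so the ratios above size a reader's likely workaround and not a planned method.
- *Leaving order out biases the comparison.* Random order already protects the contrast from period effects on average. A period term mainly helps precision and cannot remove carryover.
- *Right-ON versus left-ON is the comparison that suffers.* The hypothesis does not compare those two settings.
- *Patients are put at risk.* Nothing here concerns safety. Section 6 provides monitoring for side effects, and Section 5 returns patients to their initial settings at the end of the visit.

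Right and left may also matter in themselves: Section 2 notes that "right-hemisphere circuitry seems to be more affected than the left in patients with FOG". Recoding should therefore add to the right/left results and not replace them.

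**Conclusion.** The concern holds and should be acted on. Followed as written, Section 7 never produces the contrast stated in Section 3, and it gives no precision for any within-patient difference between settings. That much follows from the text and from the range |s1 − s2| to s1 + s2, without assumed values.

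The size of the side-label error is conditional. For p between 0.5 and 0.8, right-ON minus both-ON differs from the hypothesised effect by 50% down to 20% of the more-versus-less-affected difference, provided that the effect depends only on which hemisphere is more affected. The precision ratios depend on assumed correlations and sample sizes, and point to lost precision.

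Part 2 is not part of this conclusion. There the text says only that "During these visits the stimulation settings will be changed to one of the following conditions", with no random order stated. The freezing questionnaire and the Clinical Global Improvement Scale, both collected after each Part 2 change, are missing from Section 7, but that is secondary.

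**What to change.** Add to Section 7:

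> Part 1: each unilateral setting will be recoded as more or less affected hemisphere stimulated (contralateral to the worse body side), using the lateralised UPDRS motor items from the both-OFF, off-medication assessment at Visit 1. Ties will be resolved by side of onset. This rule is fixed before Visit 1; recoding from the screening UPDRS is a sensitivity check. The primary contrast is the within-patient difference in velocity and stride length (and UPDRS) between more-affected-hemisphere stimulation and both-ON, reported as mean, SD and 95% CI, with individual differences plotted. Contrasts of the other settings with both-ON are secondary. Right/left results are also shown descriptively. The CI will come from the paired differences, or from a mixed model with patient as random effect, setting and period as fixed effects, and Kenward-Roger degrees of freedom.

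The both-OFF assessment is the better basis for recoding. At screening the patients are already implanted, no stimulation-off state is specified, and the 12-hour medication withdrawal is asked for only afterwards, so treatment may mask the asymmetry. The primary contrast does not itself use the both-OFF data.

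The cost is a few lines of text and a standard analysis in software the plan already names, with no new visit or procedure. Limits remain: the period term cannot remove carryover when settings change hourly; individual differences rest on one assessment per setting and do not prove individual response; and the both-OFF assessment comes only one hour after the change. Paired summaries for Part 2, including the freezing questionnaire and the Clinical Global Improvement Scale, are optional.
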